8.5.2 Analysis of Primary Endpoints

Liner regression will be applied with change from baseline of HR as dependent variable and baseline HR and age as covariates at week 6, 14 and 26, respectively.

Furthermore, the mean value, standard deviation and 95% confidence interval (CI) will be calculated for the difference between HR at baseline and after week 6, 14 and 26 weeks treatment.

This analysis will be done both in FAS population and PP population.

8.5.3 Analysis of Secondary Endpoints

Same approach will be used for secondary continuous endpoints. For secondary endpoints such as SBP, DBP, NT-Pro BNP, left ventricular ejection fraction (EF%), left ventricular end-systolic dimension (LVESD), left ventricular wall thickness, E/A ratio, 6min walk test, questionnaires score, paired t test will be used to compare the difference of these parameters between baseline and after 26 week treatment directly, furthermore, 95% confidence interval will also be calculated.

The SF-36 assesses 8 health status domains (ie, physical functioning, role physical functioning, role emotional functioning, mental health, vitality, social functioning, bodily pain, and general health). Scale scores are obtained by summing the items together within a domain, dividing this outcome by the range of scores and then transforming the raw scores to a scale from 0 to 100 [29-31].

The questionnaire of Minnesota Living with Heart Failure Questionnaire (MLHF) has 21 items. Questions assess the impact of frequent physical symptoms of heart failure - shortness of breath, fatigue, swollen ankles and difficulty sleeping. Other items ask about the effects of heart failure on physical and social functions including walking and climbing stairs, household work, need to rest, working to earn a living, going places away from home, doing things with family or friends, recreational activities, sports or hobbies, sexual activities, eating foods the patient likes and mental and emotional functions of concentration and memory, worry, loss of self control, and being a burden to others. Since treatments might have direct effects on a patient's life in addition to their effects on symptoms and functional limitations of heart failure, questions about side effects of medications, hospital stays and costs of care were included to help measure the overall impact of treatments for heart failure on patients' quality of life.

Scoring: Simple summation of responses. Total score (min = 0, max = 105), physical dimension (min= 0, max = 40) emotional dimension (min = 0, max = 25); the higher the summed score, the worse is the impact of heart failure on a patient's quality of life^[32-34].

8.5.4 Analysis of Safety and Other Endpoints

All safety analyses will be performed on the safety population. AEs will be classified by Primary System Organ Class (SOC) and Preferred Term (PT) according to the Medical Dictionary for Regulatory Activities (MedDRA).

The incidence of treatment-emergent adverse events will be tabulated. In addition, the incidence of treatment-emergent AEs considered related to study medication (i.e., those AEs judged by the investigator to be either certainly, probably or possibly related to study medication and those with missing casual relationship) as well as the incidence of treatment-emergent AEs with severe or very severe intensity will also be reported.

All SAEs and those AEs leading to permanent discontinuation of study medication will be reported. Summary statistics will be provided for body weight, vital signs, ECG parameters and safety-related laboratory analyses. Summaries will consist of the number of patients assessed, sample mean value observed together with its associated standard error, sample mean change versus baseline together with its associated standard error and 95% confidence interval.

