Although clinical trials have consistently shown overall high beta-blocker tolerability, many patients even in the trial setting were unable to achieve target beta-blocker doses. For example, the mean dose of carvedilol in the Carvedilol Prospective Randomized Cumulative Survival (COPERNICUS) trial [13] was 37 mg compared with the target dose of 50 mg/d and, in the Metoprolol CR/XL Randomized Intervention Trial in Heart Failure (MERIT-HF) [14], metoprolol succinate dose on average was 159 mg as compared with the target dose of 200 mg. Only about two thirds of the patients in both these trials reached target doses. These results not only suggest that heart rate may be a major determinant of the ability to titrate beta-blocker dose and their tolerability, but that it may also serve as a therapeutic target for beta-blocker therapy.

It has been shown that beneficial effects of beta-blockers are related to the magnitude of heart rate reduction [20], which favors the selective beta1-adrenoceptor-blocker bisoprolol [21]. In CIBIS-ELD trial [22], indicates the heart rate after up-titration, predicted all-cause mortality risk in elderly

patients with chronic heart failure. Achieved resting heart rate between 55 and 64 bpm bisoprolol up-titration was associated with lower long-term mortality risk and the lowest frequency of adverse events. For every 10 bpm. increase in heart rate, a corresponding 19% increase was seen in all-cause mortality after adjusting for age, sex, beta-blocker pre-treatment, ventricular function, heart rate, and NYHA class at baseline. This finding is consistent with results from a large prospective observational survey, where 26% of the patients were uptitrated to the target dose [23].

However, up-titration is frequently associated with challenging, dose-related side effects such as hypotension, bradycardia, dizziness, and sometimes worsening of concomitant COPD, predominantly with non-selective beta-blockers [24-26]. As a consequence, recommended target doses can rarely be reached. A recent analysis demonstrates that among other dose-related effects, heart rate reduction was the major factor limiting beta-blocker up-titration to recommended doses [27].

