4.1 Primary Objectives

To explore the heart rate control (the change of heart rate) under different doses of Bisoprolol in Chinese Heart Failure patients with NYHA class II- IV.

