5.1.1 Major aspects of the trial

There will be a 2-week screening period when baseline lab tests, electrocardiogram (ECG), ultrasound cardiogram (UCG), Holter and Questionnaires will be conducted in this period. Patients who met all the inclusion criteria but none of the exclusion criteria will be enrolled. Totally 236 patients will be enrolled in the study. The anticipated period of the whole study is approximately 21 months including a 14-month recruitment period and a 26-week treatment period.

All enrolled patients will start to take oral Bisoprolol 1.25mg, once daily. All other cardiovascular medicines must be stabilized at least one month before screening period and could be continued. There will be 8 visits in total. Oral Bisoprolol needs to be started from 1.25mg (3±1weeks), up-titrated to 2.5mg (6±2weeks), 3.75mg (10±2weeks), 5mg (14±2weeks), 7.5mg (18±2weeks) with an interval of 3-4 weeks, then up-titrated to 10 mg after 8 weeks (26±2weeks). Symptoms, ECG and safety endpoints will be assessed at all visits. Lab tests will be assessed at 2.5mg (6±2weeks), 5mg (14±2weeks) and 10mg (26±2weeks). Please refer to Figure 1 for a detailed study diagram.

The Up-titration should be judged by the investigator and patients must well tolerate the previous dose. Intolerance may be defined as:

- (1) Resting heart rate < 55bpm;
- (2) Blood pressure < 90/50 millimetre(s) of mercury(mmHg);
- (3) Adverse Event (AE) lead to intolerance as judged by the investigator;

The primary endpoint is:

Resting heart rate under 2.5mg (6±2weeks), 5mg (14±2weeks) and 10mg (26±2weeks) of Bisoprolol vs at baseline

The secondary endpoints include:

- Resting heart rate at 1.25mg (3±1weeks), 3.75mg (10±2weeks), and 7.5mg (18±2weeks) vs at baseline
- Heart function detected by UCG: including LVEF, left ventricular end-systolic dimension (LVESD) and left ventricle end-diastolic dimension (LVEDD), interventricular septal thickness (IVST) and E/a ration at baseline, 5mg (14±2weeks) and 10mg (26±2weeks).
- Systolic and diastolic blood pressure, symptoms and NYHA classification at all visits.

- Proportion of patient number whose Resting heart rate < 70 and > 55 bpm at all visits
- Quality of life [based on the MOS item short form health survey (SF-36) and Minnesota Living with Heart Failure (MLHFQ)] at baseline and end of treatment.
- 6-minute walk test and N-terminal Pro-B-type Natriuretic Peptide (NT Pro-BNP) at baseline and end of treatment.

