7.4.1.2 Methods of Recording and Assessing Adverse Events

At each trial visit, the subject will be queried on changes in his/her condition. During the reporting period of the trial any unfavorable changes in the subject's condition will be recorded as AEs, whether reported by the subject or observed by the investigator.

Complete, accurate and consistent data on all AEs experienced for the duration of the reporting period (defined below) will be reported on an ongoing basis in the appropriate section of the CRF. Among these AEs, all SAEs or non-serious ADRs must be additionally documented and reported using an Adverse Event Safety Report Form as described in Section 7.4.1.4.

It is important that each AE report include a description of the event, its duration (onset and resolution dates [and times, when it is important to assess the time of AE onset relative to the recorded treatment administration time]), its severity, its causal relationship with the trial treatment, any other potential causal factors, any treatment given or other action taken (including dose modification or discontinuation of the IMP) and its outcome. In addition, serious cases should be identified and the appropriate seriousness criteria documented. If an AE constitutes a DLT this has to be documented accordingly

Specific guidance can be found in the CRF Completion and Monitoring Conventions provided by the Sponsor.

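### Section 8.5.4 plans no adverse-event table by dose at onset or by dose modification, although the trial titrates through six doses

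*Combined protocol and SAP*

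**What the plan says.** Section 8.5.4 covers adverse events in the safety population, coded by system organ class and preferred term: "The incidence of treatment-emergent adverse events will be tabulated". It then names subsets: events judged related, events of high intensity ("the incidence of treatment-emergent AEs with severe or very severe intensity will also be reported"), and finally "All SAEs and those AEs leading to permanent discontinuation of study medication will be reported". No table is described by dose, visit, titration step or time at risk.

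The rest of the plan is organised by dose. Section 4.1 sets the primary objective: "To explore the heart rate control (the change of heart rate) under different doses of Bisoprolol". Sections 8.3.1 and 8.3.2 attach resting heart rate to visits labelled 1.25, 2.5, 3.75, 5, 7.5 and 10 mg. Section 3.1.3 says that "up-titration is frequently associated with challenging, dose-related side effects such as hypotension, bradycardia, dizziness". Section 5.1.1 makes each step conditional on tolerance, and one of its three intolerance criteria is "Adverse Event (AE) lead to intolerance as judged by the investigator".

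On data capture, section 7.4.1.2 asks for onset and resolution dates for each event and for "any treatment given or other action taken (including dose modification or discontinuation of the IMP) and its outcome". Section 7.1 records use of study drug at every visit from baseline on. Section 8.3.4 lists drug exposure as a safety endpoint, but 8.5.4 does not link it to adverse events.

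**The concern.** In a forced-sequence titration, one incidence per preferred term over the whole treatment period combines events that arose at very different doses and after very different lengths of exposure. The background expects hypotension, bradycardia and dizziness to depend on dose, so a colleague reading the report would want to know at which step they appeared. The tables as described cannot answer that. Nor can they say which events led to a dose reduction or other dose change, because permanent discontinuation is the only action taken that gets its own report. The trial would then describe the heart-rate effect step by step and the adverse events only in total. If by-dose tables were requested later, the dose groupings and the rule for assigning events would be chosen with the events already in view.

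**Working it through.** **1. What 8.5.4 covers, set against what is recorded.**

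| Item | Recorded? | Planned table in 8.5.4? |
|---|---|---|
| Related, severe, serious events | Yes (7.4.1.1, 7.4.1.2) | Yes |
| Permanent discontinuation | Yes (7.4.1.2) | Yes |
| Dose modification as action taken | Yes (7.4.1.2) | None named |
| Dose at onset | Derivable: onset date (7.4.1.2) with study-drug use (7.1) | None named |
| Time at each dose | Derivable: study-drug use (7.1); exposure is an endpoint (8.3.4) | None named |
| Reason a dose was not raised | Not required by any section | None named |

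**2. Time at each dose.** The visit weeks in 7.1 are 3, 6, 10, 14, 18 and 26. If each visit closes its labelled step, the steps last 3, 6 − 3 = 3, 10 − 6 = 4, 14 − 10 = 4, 18 − 14 = 4 and 26 − 18 = 8 weeks, which sum to 26. For a patient who takes every step on time, 1.25 mg is 3/26 = 11.5% of treatment time and 10 mg is 8/26 = 30.8%. Even with a constant event rate, such a patient would be expected to have 8/3 = 2.7 times as many events at 10 mg as at 1.25 mg. Counts by dose therefore need person-time beside them. Eight weeks at 10 mg is one reading of 6.2. Sections 5.1.1 and 6.2 also give different step intervals (3-4 and 2-4 weeks), so observed rather than nominal time should be used.

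**3. How many patients may be at each dose.** Section 8.1 gives no such number, but its precision figures allow an illustration. Inputs: 236 subjects, 15% dropout, SD 10 bpm, two-sided 95%.
- From these alone: n = 236 × 0.85 = 200.6, and half-width = 1.96 × 10/√200.6 = 1.38 bpm at either week.
- The plan states 1.54 (week 6) and 2.12 (week 14), which this does not reproduce.
- Inverting: (19.6/1.54)² = 162, or 81% of 200.6; (19.6/2.12)² = 85.5, or 43% of 200.6.

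Section 8.1 mentions up-titration status without giving values. The stated figures are consistent with an unstated share of patients at the scheduled dose. An input is missing; the figures are not shown to be wrong.

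**4. What by-dose cells would look like.** If the whole gap is that share, exact (Clopper-Pearson) 95% intervals for an event in about 10% of patients are:

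| Denominator | Events | 95% CI | One-sided 95% upper bound if no events, 1 − 0.05^(1/n) |
|---|---|---|---|
| All, 236 | 24 | 6.6-14.8% | 1.3% |
| 2.5 mg, 162 | 16 | 5.8-15.5% | 1.8% |
| 5 mg, 86 | 9 | 4.9-18.9% | 3.4% |

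These cells are wider than the overall one but still readable. The 162 and 86 would be patients at the dose at one visit, so the number ever exposed could be larger. Nothing can be derived for 7.5 or 10 mg, because 8.1 makes no assumption for week 26.

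**The case against.** The strongest answer is that two of the named harms do not rest on adverse-event tables alone. Heart rate, blood pressure and ECG are taken at every visit (Appendix III). Blood pressure and the proportion with heart rate between 55 and 70 bpm are endpoints at all visits, and Holter time below 55 bpm is measured at weeks 6 and 14 and at end of treatment (8.3.2). Section 8.5.4 also summarises vital signs and ECG. This stands in part. Those are readings at scheduled visits, labelled with the scheduled dose rather than the dose taken, and they do not count symptomatic events between visits or cover dizziness.

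Second, the safety objective in 4.2 is an overall profile in an exploratory single-arm pilot, and by-dose tables confound dose with time on treatment and with tolerance of earlier doses. That is right. It limits the tables to description and keeps the point small.

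Third, 8.5.4 gives no table layout, so the absence of a dose split is inferred from silence. Section 8.4 refers to an SAP, but only for the definition of major protocol violations, and the text available contains no by-dose adverse-event plan.

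A reader might infer that the trial is unable to show harm by dose. The documents do not support that: onset dates, action taken and study-drug use are all recorded, so the gap is in the planned tables. Nor does 8.5.4 single out permanent discontinuation alone; that holds only for dosing consequences.

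**Conclusion.** The point holds as a low-cost improvement. The adverse-event tables described in 8.5.4 will not show the dose at which events arise or which events led to a dose change, and the by-visit measurements fill this only in part. This rests on reading 8.5.4 as complete, and on dose at onset being derivable from the study-drug record.

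Two further inferences are tempting and should not be made. One is a specific multiple by which the overall incidence understates the rate at the top dose. That would need event counts by dose, the share reaching 10 mg, and the dose at which the other patients spend their remaining weeks. The documents give none of these. The shares in 3.1.3 (about two thirds, and 26%) come from other programmes. The other is that events which blocked a step up could be tabulated from data already planned. No section requires the reason for not raising a dose. Two of the three intolerance criteria are heart rate and blood pressure readings, and under 7.4.1.1 abnormal findings without symptoms generally need not become adverse events.

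**What to change.** In 8.5.4 keep the overall table and add two:

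(a) Treatment-emergent adverse events, serious events, bradycardia and hypotension by the dose actually taken at onset. Give patients ever exposed to that dose and observed person-time at it as denominators. State in advance how an event on the day of a dose change, or after the last dose, is assigned.

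(b) Adverse events whose recorded action taken was dose modification.

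Label both as descriptive, with a note that dose is tied to time on treatment and that patients at higher doses are those who tolerated lower ones.

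The cost is programming and two tables, with no new visit or measurement. The downside is small cells at the top doses, where the number of patients is unknown in advance.

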5.3.2 Exclusion Criteria

Subjects are not eligible for this trial if they fulfill any of the following exclusion criteria:

- Acute coronary syndrome (ACS) within 3 months
- Under beta-blocker treatment for the last 2 weeks
- Under other medicine treatment which may affect heart rate, like Non-dihydropyridine calcium channel blockers (NDHP-CCBs) or ivabradine for the last 2 weeks; Under Digoxin treatment ($>0.125\text{mg}$)
- Uncontrolled Diabetes [hemoglobin A1c, (HbA1c) $>7.5\%$]

- Severe or uncontrolled hypertension [resting Systolic Blood Pressure (SBP) >180 mmHg, or resting Diastolic Blood Pressure (DBP) >110mmHg at screening period]
 - Severe hypotension (resting SBP<90mmHg, or resting DBP<50mmHg)
 - Resting heart rate <60 beat per minute (bpm)
 - Any contradiction to Bisoprolol according to label, including:
 - acute heart failure or during episodes of heart failure decompensation requiring i.v. inotropic therapy
 - cardiogenic shock
 - AV block of second or third degree (without a pacemaker)
 - sick sinus syndrome
 - sinoatrial block
 - slowed heart rate, causing symptoms (symptomatic bradycardia),
 - decreased blood pressure, causing symptoms (symptomatic hypotension),
 - severe bronchial asthma or severe chronic obstructive pulmonary disease
 - sever forms of peripheral arterial occlusive disease and Raynaud's syndrome
 - untreated phaeochromocytoma
 - metabolic acidosis
 - hypersensitivity to bisoprolol or to any of the excipients
 - Severe Arrhythmia including atrial fibrillation, atrial flutter, ventricular fibrillation, ventricular flutter or ventricular tachycardia
 - Significant valvular heart disease, congenital heart disease, pulmonary heart disease or perinatal heart disease
 - Acute pulmonary edema
 - Severe hepatic dysfunction, defined as:
 - Serum Alanine Aminotransferase (ALT) > triple the upper limit of the normal range; and/or
 - Serum Aspartate Aminotransferase (AST) > triple the upper limit of the normal value range and/or
 - Severe renal dysfunction, defined as:
 - Serum creatinine > twice the upper limit of the normal range
 - Chronic Kidney Disease (CKD) [glomerular filtration rate (GFR)<45 ml/min]
 - hyperthyroidism or hypothyroidism
 - Severe infectious disease, eg Human Immunodeficiency Virus (HIV) positive or active tuberculosis
 - Severe autoimmune disease, e.g. lupus erythematosus, multiple sclerosis
 - Severe respiratory, digestive, hematological disease (including Anemia of Hb <100g/L) or tumor
-

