7.1 Schedule of Assessments

Day 0 is defined as the first day of enrollment and oral Bisoprolol administration in subject.

The trial procedures and assessment contents are as follow:

1. Screening Visit/Visit 1: Day-14 to Day 0: this visit entails the following:

Before any procedures that are related to the trial is undertaken, informed consent of the patient should be obtained. Thereafter, basic information of the patient will be obtained and patients are screened for eligibility based on the inclusion and exclusion criteria.

- a) Record birth date, gender, height, weight, BMI, waist circumference, current medical condition and past medical history, including concomitant therapies
- b) Perform physical examinations, including vital signs (systolic and diastolic blood pressure, resting heart rate)
- c) NYHA classification and clinical symptoms
- d) ECG: heart rate; sinus rhythm/arrhythmia, specify; cardiac hypertrophy(yes/no); abnormal ST-T change(yes/no),if yes, specify;
- e) Echocardiography: LVEF, LVESD, LVEDD, IVST and E/A ratio
- f) Routine blood tests: full blood count (white blood cells, neutrophils, red blood cells, hemoglobin and platelets), liver function (ALT, AST), renal function (Bun, Cr), fasting blood glucose and blood lipids (TC, TG, LDL-C and HDL-C), electrolyte (K, Na) , NT Pro-BNP(data within -28 days of liver function, renal function, fasting blood glucose and blood lipids are accepted)

- g) Routine urine test(PH, Specific gravity, Protein, Glucose, Ketone, Nitrite, Leukocytes, Hemoglobin, Red blood cells, Bilirubin), urine pregnancy test
- h) Questionnaires: SF-36 and MLHFQ
- i) 6-minute walk test
- j) Holter: heart rate (24 hour, day time, night time); sinus rhythm/arrhythmia, specify; proportion of 24 hour heart rate >70 bpm, proportion of 24hour heart rate <55 bpm; proportion of arrhythmia
- k) Record adverse events, concomitant drugs/procedure;
- l) Signed the informed consent form

2. Visit 2 (Baseline) Day 0: this visit entails the following:

- a) Perform physical examinations, including vital signs (systolic and diastolic blood pressure, resting heart rate); Weight
- b) NYHA classification and clinical symptoms;
- c) ECG: heart rate; sinus rhythm/arrhythmia, specify; cardiac hypertrophy(yes/no); abnormal ST-T change(yes/no),if yes, specify;
- d) Record adverse events, concomitant drugs/procedure and use of study drug;

3. Visit 3 (1.25mg measurement) 3 ± 1 week: This visit entails the following:

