Related: Reasonably related to the IMP. AE could medically (pharmacologically/clinically) be attributed to the IMP under study in this clinical trial protocol.

Abnormal Laboratory Findings and Other Abnormal Investigational Findings

Abnormal laboratory findings and other abnormal investigational findings (for example, on an ECG trace) should not be reported as AEs unless they are associated with clinical signs and symptoms, lead to treatment discontinuation or are considered otherwise medically important by the Investigator. If a laboratory abnormality fulfills these criteria, the identified medical condition (for example, anemia, increased ALT) must be reported as the AE rather than the abnormal value itself.

- **Adverse Reaction(ADR)**

In accordance with GCP, adverse drug reaction is an adverse event considered related to drug treatment.

Serious Adverse Event

A serious adverse event (SAE) is any untoward medical occurrence that at any dose:

- Results in death.
- Is life-threatening.

NOTE: The term “life-threatening” refers to an event in which the subject is at risk of death at the time of the event; not an event that hypothetically might have caused death if it was more severe.

- Requires inpatient hospitalization or prolongation of existing hospitalization.
- Results in persistent or significant disability/incapacity.
- Is a congenital anomaly/birth defect.
- Is otherwise considered as medically important.

Note: Important medical events that may not result in death, be life-threatening, or require hospitalization may be considered as SAEs when, based upon appropriate medical judgment, they may jeopardize the subject or may require medical or surgical intervention to prevent one of the outcomes listed above. Examples of such events include allergic bronchospasm requiring intensive treatment in an emergency room or at home, blood dyscrasias or convulsions that do not result in inpatient hospitalization, or the development of drug dependency or drug abuse.

For the purposes of reporting, any suspected transmission of an infectious agent via an IMP is also considered a SAE as described in Section 7.4.1.4.

Events that Do Not Meet the Definition of an SAE

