8.5 Description of Statistical Analyses

8.5.1 General Considerations

Statistical analysis will be performed using CRF data obtained until database lock. The FAS population will be used primarily to present baseline characteristics and analyze efficacy data. Selected efficacy analyses will be repeated for the PP population.

If confidence intervals are to be calculated, 2-sided with significance level 0.05 is used, unless otherwise specified.

Continuous variables will be summarized using descriptive statistics, i.e., number of subject (N), mean, median, standard deviation (S.D.), 25th and 75th percentile (Q1-Q3), minimum and maximum. Counts of missing observation will be included in the denominator and presented as a separate category.

For all variables, the baseline value will be defined as the last measurement taken prior to the first administration of treatment drug.

The dropouts and missing data will not be imputed.

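### Section 8.5.4 plans no count of patients for abnormal laboratory values or categorical ECG findings, so an asymptomatic AV block or laboratory crossing not reported as an adverse event is counted in no planned table

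*Combined protocol and SAP*

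**What the plan says.** Section 8.5.4 names the data: "Summary statistics will be provided for body weight, vital signs, ECG parameters and safety-related laboratory analyses". It then fixes the content: "Summaries will consist of the number of patients assessed, sample mean value observed together with its associated standard error", followed by the mean change from baseline with its standard error and 95% confidence interval. It plans no count beyond a limit, shift table, laboratory grade table or ECG category table.

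Section 8.5.1 has a broader rule for continuous variables in general, which adds the median, standard deviation, "25th and 75th percentile (Q1-Q3), minimum and maximum". It gives no equivalent rule for categorical variables, apart from saying that missing observations are shown as their own category.

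Section 7.1 defines the ECG record: "ECG: heart rate; sinus rhythm/arrhythmia, specify; cardiac hypertrophy(yes/no); abnormal ST-T change(yes/no"), with free text where specification is needed. Appendix III schedules the ECG at all 8 visits. ECG does not appear among the safety endpoints in 8.3.4, so 8.5.4 is its only stated analysis.

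Section 7.4.1.1 limits the adverse event route: "Abnormal laboratory findings and other abnormal investigational findings (for example, on an ECG trace) should not be reported as AEs unless they are" accompanied by signs and symptoms, cause treatment to stop, or are otherwise judged medically important by the investigator.

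Section 5.3.2 contains limits that matter here as points of reference: "Serum Alanine Aminotransferase (ALT) > triple the upper limit of the normal range" (AST likewise), "Serum creatinine > twice the upper limit of the normal range", GFR below 45 ml/min, haemoglobin below 100 g/L, and "AV block of second or third degree (without a pacemaker"). These are eligibility criteria.

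**The concern.** The safety profile is part of the secondary objective (4.2), and the trial has one arm. Without a comparator, uncommon harms are best described by how many patients had them. A mean over about 200 patients answers a different question. It shows a shift common to the group and is nearly blind to a few patients with a large change. For rhythm type a mean does not exist at all.

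The report could therefore state that mean laboratory and ECG values did not change, and be correct on its own terms, without saying whether any patient developed AV block or how many patients passed a limit that 5.3.2 treats as severe.

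**Working it through.** The plan states no figure for this point, so there is none to reproduce. The check has four parts.

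**1. ECG items against the prescribed statistics**

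| ECG item (7.1) | Type | Mean and mean change | Minimum and maximum (8.5.1) |
|---|---|---|---|
| Heart rate | numeric | valid | valid |
| Rhythm / arrhythmia type | categorical, free text | undefined | undefined |
| Hypertrophy | yes/no | net proportion only | uninformative |
| ST-T change | yes/no | net proportion only | uninformative |

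Three of four items are not numeric. Coding yes/no as 1/0 would give a mean, but the mean change is then new cases minus resolved cases. Five new and five resolved among 200 give (5 − 5)/200 = 0. That does not show who developed the finding.

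**2. Laboratory values: what a mean reveals**

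Input from 8.1: 236 patients with 15% dropout, 236 × 0.85 = 200.6, taken as n = 200. The documents give no ULN, baseline or standard deviation for any laboratory test, so the rest is assumed. k patients rise in ALT from 0.6 to 3.5 × ULN (a rise of 2.9). All others change by 0 on average, with SD of change 0.2 to 0.5 × ULN.

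- Shift in the mean = k × 2.9 / 200.
- Standard error = √[SD² + 2.9² × (k/n)(1 − k/n)] / √n. For k = 4 and SD 0.2: √[0.04 + 8.41 × 0.02 × 0.98] / √200 = √0.2048 / 14.14 = 0.032.
- The share of trials whose 95% t interval includes zero comes from 4,000 simulations per setting.

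| k | Mean shift (× ULN) | Standard error (SD 0.2 / 0.3 / 0.5) | Interval includes zero (SD 0.2 / 0.3 / 0.5) |
|---|---|---|---|
| 1 | 0.0145 | 0.020 / 0.026 / 0.038 | 96.2% / 95.2% / 95.5% |
| 2 | 0.029 | 0.025 / 0.029 / 0.041 | 91.5% / 90.5% / 92.7% |
| 4 | 0.058 | 0.032 / 0.036 / 0.046 | 63.8% / 71.8% / 81.8% |

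Such patients are likely to exist even if the event is uncommon. The chance of at least one in 200 is 1 − (1 − p)^200, which is 63% at p = 0.5%, 87% at 1% and 98% at 2%. The maximum from 8.5.1 would show that one exists. It would not separate one patient from four.

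**3. Where an abnormal finding is counted**

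| Finding is | Adverse event tables | 8.5.4 and 8.5.1 summaries |
|---|---|---|
| symptomatic | yes | laboratory: in the mean and range; ECG category: no |
| a reason to stop treatment | yes, and reported as leading to discontinuation | same |
| judged medically important | yes | same |
| none of these | no | same |

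The last row is the gap. Two other sources do not close it. The Holter proportion of arrhythmia (8.3.2) is taken at four time points and is not specific to AV block. Appendix III lists cardiovascular events at every visit without defining them or naming a table.

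**4. Timing**

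Appendix III schedules liver and renal tests only at screening and Visit 8 (week 26), while the blood count is also taken at weeks 6 and 14. A transient liver or renal change is missed whichever summary is used.

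**The case against.** Section 8.5.1 already asks for the minimum, maximum and quartiles of continuous variables, so an extreme laboratory value should be visible. Section 5.5.1 provides for withdrawal when a clinically relevant exclusion criterion occurs that affects safety, if withdrawal is judged necessary. A finding that stops treatment becomes an adverse event under 7.4.1.1 and is tabulated under 8.5.4. Second- or third-degree AV block is among the label contraindications in 5.3.2, so an investigator would seldom call it unimportant. The 5.3.2 limits decide eligibility and are not on-treatment thresholds. Finally, GFR is not a listed test and the ECG record has no conduction field.

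Most of this stands, and it sets the size of the point. A reader might infer that laboratory and ECG harms are summarised only by means and would generally go unseen. The documents do not support that: 8.5.1 adds the range, and 5.5.1, 7.4.1.1 and 8.5.4 bring most clinically relevant cases into adverse event or discontinuation reporting.

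The objection does not remove the remainder. A range gives no count and does not apply to rhythm type. Every adverse event route depends on symptoms, on stopping treatment or on the investigator's judgement. The plan mentions a SAP for defining major protocol violations (8.4), but nothing in the text supplied sends laboratory or ECG tables there.

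**Conclusion.** The point holds in a limited form and should be corrected. For ECG, three of the four items have no suitable planned summary, and this conclusion needs no assumption. For laboratory values, the plan can show that an extreme value exists, if 8.5.1 applies alongside 8.5.4, but not how many patients crossed a limit. What is uncounted is the asymptomatic finding that did not stop treatment and was not judged medically important. The ECG gap is the wider of the two, because the range in 8.5.1 cannot help there.

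The simulation shows only that a mean is insensitive. It rests on assumed ALT levels and standard deviations and predicts nothing about event rates in this trial. Nothing here affects the primary analysis.

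**What to change.** Amend 8.5.4, for the safety population:

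- **(a) Laboratory counts.** Give the number and percentage of patients with any post-baseline value beyond the limits in 5.3.2: ALT or AST above 3 × ULN, creatinine above 2 × ULN, haemoglobin below 100 g/L. Show these by baseline status, and state how many patients had a post-baseline test. Include GFR below 45 ml/min only if it is derived from creatinine with a named formula. Say that the limits serve as reporting cut-offs and not as on-treatment rules.
- **(b) ECG categories.** Give counts at each visit and a shift table from Day 0 to post-baseline for rhythm/arrhythmia category, hypertrophy and ST-T change. Code AV block from the free-text specification, with the coding list fixed before database lock.
- **(c) Numeric items.** Keep means for these only, and reconcile 8.5.4 (standard error) with 8.5.1 (standard deviation, median, quartiles, range).

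State as a limitation that liver and renal tests are scheduled only at screening and week 26, so transient changes are not captured.

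The cost is two descriptive tables and light coding of ECG text, with no new visit or test. AV block can be counted only where sites wrote it in the specification.
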